5 GENERAL STATISTICAL METHODS

5.1 Sample size justification

Assuming a mean ABR of 18 with standard deviation (SD) = 14 in the on-demand arm (patients randomized to receive on-demand factor concentrates) and a mean ABR of no more than 4 with SD = 6 in the fitusiran treatment arm (patients randomized to receive fitusiran) in either the efficacy period or treatment period, with a sample size of 32 evaluable patients in on-demand arm and approximately 64 evaluable patients in the fitusiran treatment arm, it is projected that the study will have greater than 90% power for testing treatment difference in mean ABRs. This power estimation was based on negative binomial regression model with a 2-sided Type I error rate of 0.05.

The planned sample size is 120 randomized patients assuming a 20% drop-out rate.

5.2 General methods

All data listings that contain an evaluation date will contain a study day relative to the day of Day 1 visit when baseline assessments are performed and fitusiran first dose is given, which is designated as Day 1. The Day 1 visit date should coincide with randomization date but could occur within 3 days after the randomization. If the fitusiran first dose is given after Day 1 visit, a study day will be calculated relative to the day of first dose. Study days will be calculated as evaluation date – Day 1 visit date (or first dose date) + 1 and pre-Day 1 visit days will be calculated as evaluation date – Day 1 visit date (or first dose date). For example, the day prior to Day 1 visit will be Day –1 and the day after Day 1 visit will be Day 2, etc. There will be no Study Day 0.

Categorical variables will be summarized using counts and percentages. Continuous variables will be summarized using the number of patients (n), mean, SD, median, interquartile range (Q1, Q3), minimum value (min), and maximum value (max). The precision of the measurement for each continuous variable will be used to determine the number of decimal places to present in tables, figures and derived listings. Minimum and maximum values will be reported with the same precision as the units of measure. The other statistics will be reported to 1 greater decimal place, and the SD will be reported to 2 additional decimal places. Any values that require transformation to standard units (metric or SI) will be converted with the appropriate corresponding precision.

5.3 Computing environment

All statistical analyses will be performed using SAS statistical software Version 9.4 (or later), unless otherwise noted.

5.4 Timing of analyses

The primary efficacy and safety analyses will be performed after all patients have either completed the 9-month treatment period or withdrawn from the study.

No interim analysis is planned for this study.

5.5 Baseline definitions

Unless noted otherwise, baseline for on demand group will be defined as the last non-missing value on or before Day 1 visit. Baseline for fitusiran group is defined as the last non-missing value before 1st dose of fitusiran or the last non-missing value on or before randomization date for patients who were randomized but never exposed to fitusiran.

ECG measurements are taken in triplicate. For the on demand group, the average of the first triplicate readings on or before Day 1 visit or on screening visit will be used as baseline. For fitusiran group, the average of the last triplicate readings before 1st dose is used as baseline.

For questionnaire assessments, the last non-missing value on or before Day 1 visit will be used as baseline. For fitusiran patients, the last non-missing value on or before date of 1st dose of fitusiran or the last non-missing value on or before randomization date for patients who were randomized but never exposed to fitusiran will be used as baseline.

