variable to account for unequal follow-up time due to early withdrawal or surgery. The ratio of the bleeding rate on the fitusiran treatment arm relative to the bleeding rate on the on-demand arm and its 95% confidence interval will be presented. Sensitivity analyses will be performed to evaluate the impact of missing data under different missing data mechanisms and details will be specified in the statistical analysis plan.

The bleeding episodes in the treatment period (Day 1 to Day 246), spontaneous bleeding episodes in the efficacy period, joint bleeding episodes in efficacy period, and bleeding episodes in the onset period will be analyzed and compared using the same model as used in the primary analysis. The change from baseline in physical health score and total score of Haem-A-QOL will be analyzed using an analysis of covariance (ANCOVA) model with fixed effects of treatment arm, baseline Haem-A-QOL physical health score and total score, the number of bleeding episodes in the 6 months prior to study entry (≤ 10 vs > 10), and hemophilia type (hemophilia A or B) as covariates.

Familywise error rate will be strongly controlled for the primary endpoint and selected secondary endpoints using a fixed sequence testing procedure.

Safety results will be summarized descriptively.

Table 1: Schedule of Assessments

| Study Visit (Month) | Screening | Treatment Period | | | | | | | | | | | | AT F/U ^{b,c} |
|---|-----------|------------------|-------|-----------------|-------|---------|---------|---------|---------|---------|---------|--------|---------------------------|--------------------------|
| | | Onset Period | | Efficacy Period | | | | | | | | | | |
| | | Baseline | | Month 1 | | Month 2 | Month 3 | Month 4 | Month 5 | Month 6 | Month 7 | EOT | EOS/ ET ^{a,b} | |
| Study Day (±Visit Window) | -60 to -1 | Day 1 | 15 ±3 | 29 ±7 | 43 ±3 | 57 ±7 | 85 ±7 | 113 ±7 | 141 ±7 | 169 ±7 | 197 ±7 | 225 ±7 | 253 ±7 | 281 ±7 |
| Informed Consent/Assent | X | | | | | | | | | | | | | |
| Medical History ^d | X | | | | | | | | | | | | | |
| Demographics | X | | | | | | | | | | | | | |
| Inclusion/Exclusion Criteria | X | | | | | | | | | | | | | |
| Randomization ^e | | X | | | | | | | | | | | | |
| eDiary Training ^f | X | | | | | | | | | | | | | |
| Physical Examination ^g | X | X | X | X | X | X | X | X | X | X | X | X | X | X |
| Body Weight and Height ^h | X | X | X | X | X | X | X | X | X | X | X | X | X | X |

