| Vital Signs | X | X | X | X | X | X | X | X | X | X | X | X | X | X |
| 12-Lead ECG ⁱ | X | X | | | | | | | | | X | | X | |
| FibroScan OR FibroTest/APRI ^j | X | | | | | | | | | | | | | |
| TG Level ^{k,l} | X | X | X | X | X | X | X | X | X | X | X | X | X | X |
| Coagulation | X | X | X | X | X | X | X | X | X | X | X | X | X | X |
| Nijmegen-Modified Bethesda Assay (Inhibitor Status) | X | | | | | | | | | | | X | X ^m | |
| AT Activity Level ^{k,n,l} | X | X | X | X | X | X | X | X | X | X | X | X | X | X |
| FVIII / FIX Levels ^k | X | X | X | X | X | X | X | X | X | X | X | X | X | X |

Table 1: Schedule of Assessments

| Study Visit (Month) | Screening | Treatment Period | | | | | | | | | | | | AT F/U ^{b,c} |
|--|-----------|------------------|-------|-----------------|-------|---------|---------|---------|---------|---------|---------|-------|---------------------------|--------------------------|
| | | Onset Period | | Efficacy Period | | | | | | | | | | |
| | | Baseline | | Month 1 | | Month 2 | Month 3 | Month 4 | Month 5 | Month 6 | Month 7 | EOT | EOS/ ET ^{a,b} | |
| Study Day (±Visit Window) | -60 to -1 | Day 1 | 15 ±3 | 29 ±7 | 43 ±3 | 57 ±7 | 85 ±7 | 113 ±7 | 141 ±7 | 169 ±7 | 197±7 | 225±7 | 253 ±7 | 281 ±7 |
| Thrombophilia Screening | X | | | | | | | | | | | | | |
| Serum Chemistry ^o | X | X | X | X | X | X | X | X | X | X | X | X | X | X |
| Liver Function Tests ^p | X | X | X | X | X | X | X | X | X | X | X | X | X | X |
| Anti-Drug Antibodies ^{k,n,q} | X | X | | X | | | X | | | | | X | X ^m | |
| Hematology ^o | X | X | X | X | X | X | X | X | X | X | X | X | X | X |
| Hepatic Tests ^p | X | | | | | | | | | | | | | |
| Exploratory Biomarkers ^k | | X | | | | | X | | | | | | X | |
| Exploratory Circulating RNA (Optional) ^k | | X | | | | | X | | | | | | X | |
| Exploratory DNA Sample (Optional) ^k | | X | | | | | | | | | | | | |
| Plasma PK ^{k,r} | | X | | X | | | X | | | | X | X | | |
| Urinalysis | X | X | | | | | | | | | | | X | |
| Urine Collection for Biomarkers ^k | | X | | | | | X | | | | | | X | |
| HJHS ^s | | X | | | | | | | | | | | X ^s | |
| Patient Resource Use ^s | | X | | | | | | | | | | | X ^s | |
| EQ-5D ^s | | X | | | | | | | | | | | X ^s | |

Table 1: Schedule of Assessments

| Study Visit (Month) | Screening | Treatment Period | | | | | | | | | | | AT F/U ^{b,c} | | | |

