6.6.5 Electrocardiogram

Electrocardiogram (ECG) findings will include rhythm, ventricular rate, PR interval, QRS duration, QT interval, and QTc interval. For post-baseline assessments where ECG is performed in triplicate, the average of the 3 (or all available) readings will be used for analysis.

Corrected QT interval (QTc), if not collected, will be calculated using both Bazett's and Fridericia's correction formulas.

PR, QRS, QT, QTc and RR intervals and their change from time-matched and pre-dose baseline will be summarized for each treatment group by scheduled visit. Patients will be categorized into ≤ 450 , $>450 - 480$, $>480 - 500$, or >500 ms per their maximum post-baseline absolute QTc interval and ≤ 30 , $>30 - 60$, or >60 ms per their maximum change from baseline QTc interval. The number and percentage of patients in each category will be summarized by treatment group.

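### The SAP's ECG baseline sentence for the on-demand arm, applied literally, selects the Screening ECG, whereas the fitusiran baseline is normally the Day 1 predose ECG; one rule should be stated for both arms.

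*SAP*

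**What the plan says.** SAP 5.5 (Baseline definitions) has a general rule and a separate ECG rule. Under the general rule, "baseline for on demand group will be defined as the last non-missing value on or before Day 1 visit"; the fitusiran arm likewise takes its last value before first dose. For ECGs the arms part. In the on-demand arm, "the average of the first triplicate readings on or before Day 1 visit or on screening visit will be used as baseline". In the fitusiran arm, "the average of the last triplicate readings before 1st dose is used as baseline".

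Protocol Table 1 schedules a 12-lead ECG at Screening and at Day 1, with a Screening window of Day -60 to -1. Its ECG footnote calls for triplicate recordings. On Day 1, fitusiran patients have a predose set and a set 4 hours after the dose; on-demand patients have two sets about 4 hours apart. A general note to the table allows a Screening assessment made within 7 days before baseline to stand without being repeated.

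SAP 6.6.5 (Electrocardiogram) uses the baseline for the PR, QRS, QT, QTc and RR intervals, whose "change from time-matched and pre-dose baseline will be summarized for each treatment group by scheduled visit". It also classes each patient's maximum QTc change from baseline as ≤30, >30-60 or >60 ms, by treatment group.

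**The concern.** One arm's rule says *first* and the other's says *last*, over a span that contains more than one scheduled ECG. If the on-demand baseline is the Screening ECG, whatever happens to the intervals between Screening and Day 1 enters the change score of that arm only. The on-demand arm is the only concurrent control for these tables. An upward shift before Day 1 would raise the control arm's apparent QTc increases and could hide a difference; a downward shift could suggest one that is not there. A programmer who follows the words and one who follows the likely intent would also produce different tables from the same data.

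**Working it through.** No power, alpha or event figure bears on this point, and the plan states no ECG figure to reproduce. The check sets the rules against the schedule.

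**Inputs.** Baseline rules: SAP 5.5. ECG schedule, Screening window, paired Day 1 sets and 7-day allowance: protocol Table 1 with its notes and ECG footnote. Day numbering: SAP 5.2 ("There will be no Study Day 0"), where a day before Day 1 is numbered as its date minus the Day 1 date. Use of the baseline: SAP 6.6.5.

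**Gap between the two baselines.** With no Day 0, Day -60 lies 60 days before Day 1 and Day -1 lies 1 day before it.

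| Case | On-demand baseline | Fitusiran baseline | Gap |
|---|---|---|---|
| Literal reading | Screening set | Day 1 predose set (normally) | 1 to 60 days |
| First of the two Day 1 sets | First Day 1 set | Day 1 predose set | 0 days |
| Screening within 7 days, not repeated on Day 1 | Screening set | Screening set | None due to the rule |

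On the literal reading, the change to the later Day 1 ECG spans about 4 hours in the fitusiran arm, but 1 to 60 days plus about 4 hours in the on-demand arm. On the second reading it spans about 4 hours in both.

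**How a gap enters the tables.** Let S, B and V be an on-demand patient's values at Screening, at the first Day 1 set and at a later reading. Then

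V - S = (V - B) + (B - S).

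The literal rule adds B - S to every on-demand change and nothing to the fitusiran changes. The fitusiran-minus-on-demand difference in mean change therefore moves by minus the mean of B - S. If that mean is zero, the difference in means does not move.

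B - S is the same at every later reading of one patient. Over the same set of readings,

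max(V - S) = max(V - B) + (B - S).

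So the tabulated maximum moves by that patient's own B - S, and patients near 30 or 60 ms can change category even when the average shift is zero. The documents give no QTc variability and no Screening-to-Day-1 shift, so neither effect can be given a number.

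**Whether other text settles it.** SAP 6.6.5 refers to a predose baseline, but on-demand patients receive no dose, and SAP 5.5 does not define the time-matched baseline. The visit windows in SAP 5.10 reallocate post-baseline measurements and exempt ECGs. Nothing else ranks Day 1 against Screening for the on-demand arm.

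**The case against.** There is a good case that the sentence is loosely worded rather than wrongly conceived. On-demand patients have two Day 1 sets, and the general last-value rule would pick the later one, which does not correspond to the fitusiran predose set. An exception was needed, and *first* supplies it. If *first* already meant Screening, the closing mention of the screening visit would be redundant; read as a fallback, it has work to do and fits the 7-day allowance. The predose and time-matched language of SAP 6.6.5 also sits better with a Day 1 baseline.

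This stands as evidence of intent. It is why the departure from the general rule is not itself an error. It does not settle the text, because to reach that meaning the reader must narrow a span that runs up to Day 1 to Day 1 alone, and turn a bare *or* into *only if missing*. No order of preference is written.

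A reader might go further and infer that the plan does measure QTc change from different time points in the two arms, or that the cardiac safety comparison is biased by some known amount. The documents support neither. The mismatch follows only from the literal reading, which is probably not the intended one, and any shift has unknown size and sign.

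**Conclusion.** The point holds as a defect of specification. The on-demand ECG baseline is ambiguous and, taken at its word, is not comparable with the fitusiran baseline: the gap is 1 to 60 days on the literal reading and 0 days on the likely intended one. This assumes that ECGs were taken as scheduled at both Screening and Day 1. Where Screening fell within 7 days and was not repeated, the rule makes no difference between the arms.

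The reach is limited to descriptive tables of ECG change by visit and the QTc change categories, with no test attached. Absolute QTc categories do not use a baseline, and efficacy, alpha and power are untouched. It is worth correcting because the control arm's change scores depend on the choice and the correction is trivial.

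**What to change.** Replace the ECG sentences in SAP 5.5 with one rule. The on-demand baseline is the mean of the first of the two Day 1 triplicate sets. The fitusiran baseline is the mean of the last triplicate set before first dose. In either arm, the last Screening triplicate is used only when the Day 1 (predose) set is missing or was not repeated. Naming the *last* Screening set matters because the protocol permits rescreening, so a patient may have more than one.

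The cost is one sentence in the SAP and the matching line in the derivation specification. No new data, visits or analyses are needed.

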5.6 Randomization stratification factors

Randomization for this study is stratified by the number of bleeding episodes in the 6 months prior to study entry (≤ 10 vs > 10) and hemophilia type (hemophilia A or B).

5.7 Multiple comparisons/multiplicity

To control for the familywise error rate at 0.05 level in the testing of primary and selected secondary endpoints, a hierarchical testing approach will be used. The endpoints will be tested in the following order:

Global protocol	US protocol	2-Sided alpha
1. ABR in the efficacy period	1. ABR in the treatment period	0.05
2. ABR in the treatment period	2. ABR in the efficacy period	0.05
3. Annualized spontaneous bleeding rate in the efficacy period		0.05
4. Annualized joint bleeding rate in the efficacy period		0.05
5. Change in Haem-A-QOL physical health score and total score in the treatment period		0.05

If testing of any of the endpoints is not statistically significant, formal testing of subsequent endpoints will stop and the null hypothesis for subsequent tests will not be rejected. For endpoint 5, change in Haem-A-QOL physical health score in the treatment period will be tested first followed by change in Haem-A-QOL total score in the treatment period. The testing of the secondary endpoint ABR in the onset period will not be included in this hierarchical testing procedure.

5.8 Missing data

On the eDiary device, it is not possible to leave questions unanswered or to enter partial data.

In the bleeding diary pages of the CRF, it is possible to have missing time of a treatment or a bleed. In that case, it is assumed that the bleeds and treatments with missing time occurred at 12:00 am.

Additional details will be included in the sections describing the analyses corresponding to each endpoint.

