7.2. Efficacy Assessments

Bleeding Episode Definitions

A bleeding episode is defined as any occurrence of hemorrhage that requires administration of factor concentrates or BPA infusion, eg, hemarthrosis, muscle, or mucosal bleeding episodes. Since bleeding episodes are recorded as an efficacy assessment of fitusiran, these will not be treated as AEs unless they meet any of the SAE criteria listed in Section 7.5.6.1.

The definition of bleeding episode types described below is based on consensus opinion of International Society on Thrombosis and Hemostasis (ISTH) as reflected in a recent publication.[10]

The start time of a bleeding episode will be considered the time at which symptoms of a bleeding episode first develop. Bleeding, or any symptoms of bleeding at the same location, that occurs within 72 hours of the last injection used to treat a bleeding episode at that location will be considered a part of the original bleeding event, and will count as one bleeding episode towards the ABR. Any bleeding symptoms that begin more than 72 hours from the last injection used to treat a bleeding episode at that location will constitute a new bleeding event.

A spontaneous bleeding episode is a bleeding event that occurs for no apparent or known reason, particularly into the joints, muscles, and soft tissues.

A joint bleeding episode is characterized by an unusual sensation in the joint (“aura”) in combination with 1) increasing swelling, or warmth over the skin over the joint, 2) increasing

pain, or 3) progressive loss of range of motion or difficulty in using the limb as compared with baseline.

A muscle bleed may be characterized by pain, swelling and loss of movement over the affected muscle group.

A target joint is defined as a joint where 3 or more spontaneous bleeding episodes in a single joint within a consecutive 6-month period has occurred; where there have been ≤ 2 bleeding episodes in the joint within a consecutive 12-month period the joint is no longer considered a target joint.

A traumatic bleeding episode is one that is caused by a known injury or trauma. Bleeding episodes sustained during sports and recreation will be counted as traumatic bleeding episodes, but patients will be asked to indicate in the eDiary that the event occurred during such activities. Training will be provided on this and other aspects of eDiary use (see Section 7.2.1).

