6.3 Efficacy analysis

Bleeding Episode Definitions

The primary source of bleeding data will be the eDiary. Additional bleeding data may be captured from the bleeding diary pages of the CRF, if not reported in the eDiary. Any other sources of bleeding data will be discussed in the CSR.

A bleeding episode is defined as any occurrence of hemorrhage that may require administration of BPA or factor. A traumatic bleeding episode is one that is caused by a known injury or trauma. Bleeding episodes sustained during sports and recreation will be counted as traumatic bleeding episodes.

Bleeding or any symptoms of bleeding at the same location that occur within 72 hours of the last injection used to treat a bleed or 72 hours after an untreated bleed at that location will be considered a part of the original bleeding event, and will count as one bleeding episode. Any bleeding symptoms that begin more than 72 hours from the last injection used to treat a bleed or 72 hours after an untreated bleed at that location will constitute a new bleeding event.

Traumatic bleeds that occur in different locations simultaneously (same date/time) in the same patient will be considered as one bleeding episode. Spontaneous bleeds that occur simultaneously (same date/time) in different locations in the same patient will be considered as separate bleeds.

Efficacy analysis will focus on observed data as collected, unless otherwise specified. Patients who discontinue study drug during the study will be strongly encouraged to continue study participation including the recording of bleeding episode data. Only bleeding episodes that are treated will be include in the primary analysis of endpoints evaluating bleeding.

Efficacy Period and Treatment Period

In the protocol, for the purpose of ABR calculation, fitusiran “Onset Period”, “Efficacy Period” and “Treatment Period” are defined. The Onset Period is defined as the first 28 days after the first dose of fitusiran, during which the AT lowering capacity of fitusiran is increasing but has not yet reached therapeutic levels. The Efficacy Period is defined as starting on Day 29 when the AT lowering capacity of fitusiran has achieved therapeutic target range. The Treatment Period is defined as the onset period plus the efficacy period. The window for each period is summarized in the table below. The corresponding window is applied to on-demand arm for analysis purpose.

	Fitusiran arm/On-demand arm

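### Setting untimed CRF injections to 12:00 am can place an injection before the bleed it treated and, at a gap of exactly three calendar dates, split one episode into two

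*SAP*

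**What the plan says.** SAP 5.8 separates two sources. For the eDiary, "On the eDiary device, it is not possible to leave questions unanswered or to enter partial data". For the CRF, "In the bleeding diary pages of the CRF, it is possible to have missing time of a treatment or a bleed", and then "it is assumed that the bleeds and treatments with missing time occurred at 12:00 am". SAP 6.3 ranks the sources: "The primary source of bleeding data will be the eDiary", and "Additional bleeding data may be captured from the bleeding diary pages of the CRF, if not reported in the eDiary".

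SAP 6.3 also sets the counting rules. "Bleeding or any symptoms of bleeding at the same location that occur within 72 hours of the last injection used to treat a bleed" belong to the original episode. Protocol 7.2 gives the other side of the same clock: "Any bleeding symptoms that begin more than 72 hours from the last injection used to treat a bleeding episode at that location" count as a new event. A separate SAP rule uses exact times: "Traumatic bleeds that occur in different locations simultaneously (same date/time) in the same patient will be considered as one bleeding episode". Simultaneous spontaneous bleeds at different sites stay separate. Only treated bleeds enter the primary analysis.

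SAP 5.8 refers to the endpoint sections for further detail. Those sections do not say how an imputed time enters these rules, do not flag imputed times, and give no sensitivity analysis for them.

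**The concern.** The imputation always moves an event to the start of its date, while the counting rules work in hours or on identical times. If the injection is untimed, the clock starts too early. If the bleed is untimed, the bleed appears too early. The same uncertainty is therefore resolved in opposite directions depending on which field is blank.

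One case is more than a convention. When the onset is timed and the injection on that date is not, midnight puts the treatment before the event it treated. That order is impossible, and the record itself shows it.

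At stake is the bleed count, the numerator of the primary endpoint and of every bleeding-rate secondary endpoint.

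**Working it through.** **The plan's own figure.** The documents give no figure for the time imputation. The power statement (SAP 5.1) is used below, so it is reproduced first, with ABR 18 (SD 14) in 32 on-demand patients and ABR 4 (SD 6) in 64 fitusiran patients. SE of the log rate ratio = √(14²/(32×18²) + 6²/(64×4²)) = √(0.0189 + 0.0352) = 0.2325. With |ln(4/18)| = 1.504, power = Φ(1.504/0.2325 − 1.96) > 0.999, consistent with the stated value above 90%.

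**Where the 72-hour count can change.** Let the injection and the next same-location symptom be D calendar dates apart, at clock times a and b (hours, 0 to under 24).

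| | Gap (h) | D ≤ 2 | D = 3 | D ≥ 4 |
|---|---|---|---|---|
| True | 24D + b − a | merge | split if b > a, else merge | split |
| Injection untimed | 24D + b | merge | split (unless b = 0) | split |
| Bleed untimed | 24D − a | merge | merge | split |
| Both untimed | 24D | merge | merge | split |

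Only D = 3 can go wrong. With a and b uniform over the day, or uniform over 07:00–23:00 (both assumed), each kind of missing time is wrong in 50% of D = 3 pairs. An untimed injection produces false splits; an untimed bleed, or both untimed, produces false merges. A simulation of 10⁶ draws for D = 1 to 6 gave 50% at D = 3 and 0 elsewhere.

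**The impossible order.** Onset Day 60 16:00, injection on Day 60 without a time, symptoms at the same site Day 63 10:00.
- The true injection time is 16:00 or later, so the true gap is at most 8 + 24 + 24 + 10 = 66 h: one episode.
- Imputed injection Day 60 00:00: gap = 72 + 10 = 82 h, so two episodes.
- Injection set to the onset, 16:00: gap 66 h, so one episode.

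**How much the onset time helps.** Take D = 3, a timed onset at clock time o, and a same-day injection at a ≥ o. The SAP rule errs when b ≤ a. Using the onset as the injection time errs only when o < b ≤ a, and then only as a false split. Assumptions: exponential delay from onset to injection with mean 1–8 h, restricted to same-day injections; onset and symptom times uniform.

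| Clock times | SAP rule wrong | Onset time used, wrong |
|---|---|---|
| 00:00–24:00 | 52–60% | 4–20% |
| 07:00–23:00 | 55–65% | 6–25% |

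**Same-time rule.** Two untimed traumatic bleeds at different sites on one date always become identical in time and merge. If only one is untimed, a truly simultaneous pair is split, unless the recorded time is 12:00 am. Spontaneous bleeds are unaffected.

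**Size.** The efficacy period, Day 29 to Day 246, is 218 days, so one episode changes a patient's ABR by 365.25/218 = 1.68. Going from 2 to 3 episodes moves the ABR from 3.35 to 5.03, across the boundary at 5 used in SAP 6.3.2.4. Planned counts are 18×218/365.25 = 10.7 per on-demand patient and 4×218/365.25 = 2.4 per fitusiran patient, or about 344 and 153 in 32 and 64 patients.

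As a one-directional bound, suppose a share f of all bleeds is miscounted, too many on demand and too few on fitusiran. The rate ratio 4/18 = 0.222 then becomes 4(1+f)/(18(1−f)): 0.227 at f = 1%, 0.246 at 5% and 0.272 at 10%. Power stays above 0.999 in each case.

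**The case against.** The strongest case for leaving the text alone is that the problem is contained. The eDiary is the main source and cannot hold partial data. CRF pages only fill gaps, and protocol 7.2.1 has sites review diary records at least every two weeks. Any convention for an unknown time will be wrong for some records, and the SAP's errors run both ways. A blanket calendar-date rule would do little better: it gives the SAP's own answer when the bleed is untimed, and when a same-day injection is untimed it exchanges false splits for false merges (35–48% wrong under the assumptions above).

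Most of this stands, and it is why the convention can be kept for records that are truly ambiguous. It does not cover the timed onset with an untimed same-day injection, where recorded data rule out the imputed order.

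Three stronger readings are tempting, and the documents support none of them.
- That untimed records are counted wrongly as a rule. Under the 72-hour clock only a three-date gap is exposed, and most untimed records will have no such neighbour.
- That the treatment comparison is biased in a known direction. Errors go both ways, and nothing is given on untimed records by arm.
- That a bleed whose injection is placed before it would be classed as untreated and leave the primary analysis. Nothing ties treated status to clock order, and the eDiary prompts for the reason for each dose.

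**Conclusion.** The point holds in a limited form. The midnight rule can miscount episodes under the 72-hour clock, but only at a gap of exactly three calendar dates. Its one clear error is to place a same-day injection before the recorded onset of the bleed it treated. The percentages rest on assumed clock times and delays; the 66 h against 82 h example needs no such assumption.

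The expected effect on the ABR ratio is small, because only untimed CRF records with a three-date neighbour, or same-date traumatic bleeds at different sites, are exposed. That is a judgement, since the documents do not give the share of such records. Even the 10% one-directional bound would not threaten the primary conclusion under the planning values. Individual ABRs are more exposed, at 1.68 per episode. This is a worthwhile correction, not a threat to the trial.

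**What to change.** In SAP 5.8, add that a missing injection time is imputed no earlier than the recorded onset of the bleed it treats: use the onset time if both fall on the same date, and 12:00 am only if the injection is on a later date or the onset is also untimed.

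For records that remain ambiguous, keep the SAP convention. These are an untimed bleed, or both times missing, at a three-date gap, and untimed same-date traumatic bleeds at different sites. An untimed injection on a later date than the onset, at a three-date gap, belongs with them. Report their number by arm and count them both ways in a sensitivity analysis.

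The cost is one sentence for the rule, a short addition for the count and sensitivity analysis, and minor programming. It should be settled before database lock, because in an open-label trial a later change to the counting rule could look data-driven.
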